10.3.1 Subjects Transitioning from Other BAX 855 Studies

Subjects transitioning from other BAX 855 studies^{ix} can use the end of study assessments in their previous BAX 855 study for screening visit assessments in this PK-guided study. Any additionally required screening assessments will be performed the same day. Subjects will return to the study site no later than 56 days for the conductance of the PK assessment, if applicable, provided eligibility has been confirmed. At the screening visit the subject will be supplied with study IP of study 261303. Until the baseline visit subjects will be treated according to their previous BAX 855 treatment regimen.

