13.4 Untoward Medical Occurrences

Untoward medical occurrences occurring before the first exposure to IP are not considered AEs (according to the definition of AE, see Section 13.2). However, each **serious** untoward medical occurrence experienced before the first IP exposure (i.e., from the time of signed informed consent up to but not including the first IP exposure) will be described on the AE CRF (and SAE Report Form if eCRF is not available). These events will not be considered as SAEs and will not be included in the analysis of SAEs.

For the purposes of this study, each non-serious untoward medical occurrence experienced by a subject undergoing study-related procedures (e.g., during blood sampling) before the first IP exposure will be recorded on the AE CRF; these events will not be considered as AEs and will not be included in the analysis of AEs.

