21.2 Detailed Flow Diagram of Study Procedures

Before **any** study procedures are performed, informed consent must be obtained from each subject.

Screening Visit

The screening procedures differ according to whether the subject is **transitioning from a previous BAX 855 study** (see Section A) or is newly recruited (see Section B). If the sponsor decides a transitioning subject requires a PK Assessment, then from the screening visit onwards procedures are identical to those for newly recruited subjects. If no PK Assessment is required, the next visit for transitioning subjects is the Baseline Visit once randomization is performed.

Evaluations must be completed within 56 days of the screening visit.

No washout is required but whenever possible the screening visit should be scheduled shortly before the next scheduled prophylactic infusion when baseline FVIII trough levels are reached in case the subject receives prophylactic treatment.

A: Subjects transitioning from other BAX 855 studies

The screening visit coincides with the end of study visit of the previous BAX 855 study; the subject must not be actively bleeding. If applicable, BAX 855 will be administered for IR determination based on the protocol of the previous study.

Informed consent must be obtained at enrollment at the latest (prior to any study-specific procedure); to give the subject sufficient time to review the ICF, this document should preferably be provided prior to the end of study visit of the previous study.

The relevant data obtained at the end of study visit of the previous BAX 855 study will be transcribed to the screening visit eCRF of this PK-guided dosing study, and where possible, duplication of blood draws or evaluations will be avoided.

The following procedures will be performed:

Clinical Assessments:

- Assessment of inclusion/exclusion criteria
- PROs (or can be done at Baseline visit) should be determined prior to any other study specific procedures:
 - Haemo-SYM questionnaire
 - EQ-5D
 - SF-36
 - Physical activity questionnaire
 - Health Resource Use

Laboratory Assessments:

Blood will be drawn for the following additional assessments:

- Screening tests:
 - CD4 count in subjects who are HIV positive
 - Viral serology (if any positive, test to be confirmed with a second sample) :
 - HIV: HIV-1 and HIV-2 Ab
 - HBV: HBsAg, HBsAb, HBcAb
 - HCV: HCVAb (PCR to be performed if positive)
- Pregnancy test, if applicable

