4.2 Safety Analysis Set (SAS)

The safety analysis set (SAS) is to comprise all subjects in the ENR with at least one BAX 855 infusion. All safety analyses will be performed on the SAS.

Information on dosing with BAX 855 is obtained from the following eCRF panels:

- *Study Infusion (both ERT Integration and Missed and on site infusions).*
- *Infusion for Determination of Incremental Recovery.*
- *Infusion for PK Assessment.*

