8.1 Adverse Events

Subject listings will be presented for all AEs using the SAS with breakdowns by seriousness and occurrence before of after first infusion of BAX 855. Summary tables of AEs that occurred during of after first infusion BAX 855 will be presented using the SAS including breakdowns by relationship to BAX 855, seriousness and severity.

The following information items are obtained from the eCRF:

- Adverse event details per subject (Adverse Events eCRF panel).
- Date and time of BAX 855 administration (Study Infusions eCRF panels).
- Reason for not completing the study (Study Completion/Termination eCRF panel).

Adverse events are coded using the Medical Dictionary for regulatory activities (MedDRA) as documented in the Data Management documentation at the time of performing the analysis.

The following derivations will be made based of the eCRF reported results:

- AEs are considered to have occurred during or after BAX 855 administration if:
 - The known start date and/or time of the AE is equal to or after the date and/or time of first BAX 855 administration in the current study, which is defined for safety analysis purposes as the PK-infusion for dose determination.
 - The eCRF question “When did event occur in relation to treatment with BAX 855 ?” has a response of any of the following:
 - During PK infusion.
 - Within 24 hours after PK infusion.
 - After more than 24 hours from PK infusion.
 - Before first treatment with BAX 855.
 - During BAX 855 treatment.
 - Within 24 hours after last BAX 855 treatment.
 - After more than 24 hours from last BAX 855 treatment.

- Time since last BAX 855 infusion should be determined as:

$$\textit{Time} = [\textit{Start Date/Time of AE}] - [\textit{Date/Time of Last BAX 855 Infusion}]$$

where the date/time of last BAX 855 exposure is the last possible BAX 855 administration, regardless of reason, prior to the start of the AE. Time since last BAX 855 infusion should only be determined if the full start date (regardless of whether time is known or not) of the AE is known. Time since last BAX 855 infusion will be presented in either hours or days, based on the following criteria:

- Presented in hours if start time of AE is known and time since last BAX 855 infusion is < 24 hours.
 - Presented in days if start time of AE is known and time since last BAX 855 infusion is \geq 24 hours.
 - Presented in days if start time of AE is not known.
- Duration of AE should be determined as:

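### The SAP rule for on-treatment adverse events can misclassify events: it dates first exposure from a PK infusion that is not always the first dose, and it counts a before-treatment answer as on-treatment

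*SAP*

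**What the plan says.** **The SAP rule.** SAP 8.1 states the scope of the tables: "Summary tables of AEs that occurred during of after first infusion BAX 855 will be presented using the SAS", that is, the Safety Analysis Set. It introduces the rule with "AEs are considered to have occurred during or after BAX 855 administration if" and then gives two limbs.

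- *Date limb:* a known onset at or after the "first BAX 855 administration in the current study, which is defined for safety analysis purposes as the PK-infusion for dose determination".
- *Answer limb:* any of seven listed answers to an eCRF question on timing relative to BAX 855. In order, three refer to the PK infusion, the fourth is "Before first treatment with BAX 855", the fifth is during treatment, and the last two follow the last treatment.

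Nothing says whether the limbs combine as AND or OR.

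**The analysis set.** SAP 4.2: "The safety analysis set (SAS) is to comprise all subjects in the ENR with at least one BAX 855 infusion". The infusion may come from the study infusion, incremental recovery or PK infusion forms.

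**The protocol's start of counting.** Section 13.2.4 counts AEs from first exposure to IP. Section 13.4 has sites enter some earlier events on the AE form but keeps them out of the analysis. Of the serious ones it says "These events will not be considered as SAEs and will not be included in the analysis of SAEs", and it treats the non-serious ones in the same way.

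**Transitioning subjects.** Protocol 10.3.1: "At the screening visit the subject will be supplied with study IP of study 261303". They continue their previous BAX 855 regimen until baseline. Protocol 21.2 adds: "If no PK Assessment is required, the next visit for transitioning subjects is the Baseline Visit once randomization is performed".

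**The concern.** Occurrence of AEs and SAEs is the first secondary safety outcome (Protocol 8.4.2.2, SAP 3.1.2.2), and the AE summary tables depend on this rule. Because Protocol 13.4 puts some pre-exposure events on the same form as true AEs, the derivation has to separate the two.

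The rule is open to error in two places. Its anchor is one particular infusion, which for transitioning subjects need not be the first in the study and need not take place at all. And one of its qualifying answers, on its face, describes an event that should be left out. With no connector stated, two programmers working from the same data could produce different AE tables. SAP 5.8, which lists changes from the protocol's analysis, does not mention a different starting point for AEs.

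**Working it through.** There is no figure to reproduce. The check applies the rule, under each connector, to three cases that the protocol allows.

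**Inputs**

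1. Correct classification: AEs count from first IP exposure (Protocol 13.2.4), and earlier events stay out (Protocol 13.4).
2. First exposure in newly recruited subjects is the PK infusion. They stay on their own FVIII product until baseline apart from that one dose (Protocol 10.3.2).
3. First exposure in transitioning subjects is the first infusion of 261303 product dispensed at screening (Protocol 10.3.1; 21.3, footnote o). For anyone who infuses it before the PK visit, the PK infusion is not the first administration in this study, even if a PK assessment is done.
4. A PK infusion is not certain. Protocol 12.1 describes an initial PK in all subjects, but its footnote makes a repeat conditional on the sponsor's evaluation where an earlier PK exists, and Protocol 21.2 sets out the route with none.

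**Result, with the before-treatment answer read literally**

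| Case | Should count? | Date limb | Answer limb | OR | AND |
|---|---|---|---|---|---|
| A. Newly recruited; event after consent, before the PK infusion, recorded under 13.4 | No | Not met | Met by the before-treatment answer | Counted: wrong | Not counted: right |
| B. Transitioning, no PK infusion; event during prophylaxis | Yes | Cannot be met, no anchor date | Met by the during-treatment answer | Counted: right | Dropped: wrong |
| C. Transitioning; event after a first 261303 dose, before the PK infusion | Yes | Not met | Depends on the answer the site chose | Depends on the answer | Dropped: wrong |

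On the literal reading, OR fails case A and AND fails cases B and C.

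**The more favourable reading.** Suppose the before-treatment answer means after the PK infusion and before first prophylaxis. Under OR, case A is then no longer admitted by that answer and B is still counted. Case C still rests wholly on the site's answer, because the anchor is later than first exposure.

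**Consistency within the SAP.** A subject who has only infused product dispensed at screening is in the Safety Analysis Set under SAP 4.2, and so in the denominator, but can never meet the date limb.

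**Missing onset dates.** The date limb needs a known onset. Protocol 14.3.2 imputes a completely missing AE onset as the date of first study drug. SAP 5.5.3 covers only causality and severity, and SAP 5.5 rules out imputation beyond what it specifies. Under AND, an event with no known onset would also be dropped.

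**The case against.** Much can be said for a benign reading.

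- **OR is the more natural connector.** The date limb is confined to known onsets, which suggests that the answer limb is the alternative when the date is unknown. Where the SAP wants every criterion satisfied, as for inhibitor development in SAP 8.3, it says so. Under OR a subject without a PK infusion still qualifies through the during-treatment answer. This stands.
- **The before-treatment answer may be legitimate.** It comes after the three PK answers and ahead of the during-treatment answer, which fits the interval between the PK infusion and first prophylaxis. A reader might infer that this meaning is impossible because the answer for more than 24 hours after the PK infusion already covers that interval. But that answer has no stated end and also overlaps the later answers, so overlap settles nothing. The eCRF, which SAP section 13 cites through the annotated study book, is not among the documents. This also stands, though the SAP gives no such definition.
- **Subjects without a PK infusion may be few or none.** Protocol 21.2 permits the route but does not say that anyone took it, and SAP section 2 describes an initial PK for enrolled subjects. This stands for case B. It does not answer case C.
- **The consequences are limited.** AE outcomes are descriptive (Protocol 14.4.2), all AEs are listed, and SAE reporting and the stopping rules do not use this flag. This stands and bears on severity. The listings are, however, also to be split by occurrence before or after first infusion, so the same definition matters there.

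**Conclusion.** The concern holds as a defect in a stated rule that can misclassify AEs. The firmest part is the anchor. For transitioning subjects who use 261303 product before the PK visit, or who have no PK infusion, it departs from Protocol 13.2.4 and from SAP 4.2 whichever connector is meant. The undefined answer and the absent connector add a second route to error: wrong inclusions under OR read literally, wrong exclusions under AND.

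Three stronger readings are not supported.

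- *That the rule both admits pre-exposure events and drops on-treatment ones.* These are alternatives under different connectors.
- *That subjects without a PK infusion lose all their AEs over 12 months.* That needs AND, the less natural reading, and at least one such subject.
- *That about 12% of AEs are affected.* The 56-day limit from screening to PK assessment (Protocol 10.3.1), set against 15 to 16 months of participation, gives 56/487 = 11.5% to 56/456 = 12.3%. That is a maximum share of calendar time, not of events. Before exposure, only serious events and non-serious events during study procedures reach the AE form.

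The number of events affected cannot be computed, because the documents give neither the number of transitioning subjects, nor how many had no PK infusion, nor the full eCRF answer list. The conclusion assumes that at least some transitioning subjects infuse the product dispensed at screening before any PK visit. Severity: should-fix. The tables are descriptive and the primary endpoint is untouched.

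**What to change.** Amend SAP 8.1 as follows.

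1. Define an on-treatment AE as one with onset on or after the date and time of the first BAX 855 infusion of any kind under 261303: product dispensed at screening, the PK infusion or the baseline infusion, whichever comes first.
2. Remove the before-treatment answer from the qualifying list. If the eCRF means the interval after the PK infusion and before first prophylaxis, say so explicitly instead.
3. Let a full onset date and time decide. Use the eCRF answer only when onset is missing or partial. This also settles the AND/OR question.
4. Reconcile this with Protocol 14.3.2 for completely missing onset dates, stating whether the eCRF answer or the protocol's imputation prevails.
5. Record in SAP 5.8 any remaining difference from the protocol.

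The cost is a few lines of SAP text and one derivation in the AE analysis dataset. Infusion records (the diary is issued at screening, Protocol 10.5) and the eCRF answers are already collected.

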8.2 Clinical Laboratory Evaluations

Subject listings will be presented on laboratory data from the following sources using the SAS which would include breakdowns for clinically significant values:

- Central laboratory.
- Central laboratory from previous BAX 855 study.
- Local laboratory.

Summary and shift tables will be presented using the SAS for central laboratory assessments broken down by laboratory department:

- Haematology.
- Clinical chemistry.
- Lipids.
- Viral serology.

Box-plots containing descriptive statistics of central laboratory assessments will be presented using the SAS for the following laboratory departments by age group and treatment arm across visits:

- Haematology.
- Clinical chemistry.
- Lipids.

All laboratory summary tables should be presented by age group and alphabetic assessment name.

Results from the central laboratory will be included in the reporting for this study. Results will be presented using CDISC compliant terms and standard international (SI) units.

The following table provides a list of the different laboratory assessments and their respective departments that are expected to be received from the central laboratory:

Table 11 List of Laboratory Assessments

Department	Assessment Name	Standardized International (SI) Unit
Chemistry	Alanine Aminotransferase (ALT)	U/L
	Aspartate Aminotransferase (AST)	U/L
	Albumin	g/L
	Alkaline Phosphatase	U/L
	Blood Urea Nitrogen (BUN)/Urea	mmol/L
	Bicarbonate	mmol/L
	Chloride	mmol/L
	Creatinine	umol/L
	Glucose	mmol/L
	Potassium	mmol/L
	Sodium	mmol/L
	Total Bilirubin	umol/L
	Total Protein	g/L
	Coagulation	activated Prothrombin Time (aPTT)
von Willebrand Factor Antigen (vWFA)		%vWF:Ag
HCV Quantitative PCR	Hepatitis C (HCV) Ribonucleic Acid (RNA) Quantitative Polymerase Chain Reaction (PCR)	IU/mL
Haematology	Anisocytosis	
	Basophils/Leukocytes	%
	Basophils	x10E9/L
	Elliptocytes	
	Eosinophils/Leukocytes	%
	Eosinophils	x10E9/L
	Haematocrit	L/L
	Haemoglobin	g/L
	Hypochromasia	
	Large Platelet	
	Lymphocytes/Leukocytes	%
	Lymphocytes	x10E9/L
	Ery. Mean Corpuscular Haemoglobin Concentration (MCHC)	g/L
	Ery. Mean Corpuscular Volume (MCV)	fL

Department	Assessment Name	Standardized International (SI) Unit
	Macrocytosis	
	Microcytosis	
	Monocytes/Leukocytes	%
	Monocytes	x10E9/L
	Neutrophils/Leukocytes	%
	Neutrophils	x10E9/L
	Platelet Count	x10E9/L
	Red Bloodcell Count (RBC)	x10E12/L
	Target Cells	
	White Bloodcell Count (WBC)	x10E9/L
Lipids	Cholesterol	mmol/L
	High-density Lipoprotein (HDL) Cholesterol	mmol/L
	Low-density Lipoprotein (LDL)-C	mmol/L
	LDL Cholesterol	mmol/L
	Triglycerides	mmol/L
	Very Low Density Lipoprotein (VLDL) Cholesterol	mmol/L
	VLDL-C (direct LDL)	mmol/L
Genetics	HLA-DQB1 Allele 1	
	HLA-DQB1 Allele 2	
	HLA-DRB1 Allele 1	
	HLA-DRB1 Allele 2	
TBNK Assay	CD3+CD4+ Percentage	%
	CD3+CD4+ Absolute	Cells/uL
Viral Serology	Hepatitis B Surface Antigen (HBsAG)	
	HIV ½ Antibody	
	Hepatitis B Antibodies (Anti-HBs)	
	Hepatitis C Virus Antibodies (Anti-HCV)	
	Anti-HIV ½	
	Total Hepatitis B Virus Core Antibodies (Anti-HBc)	
Note: Laboratory assessments with no entry in the SI unit column do not have a quantitative unit and would have results such as "+1" or trace for example.		

8.2.1 Safety Laboratory Assessments

The following information items are obtained from the eCRF:

- Information from the Investigator on abnormal results is obtained from the eCRF (Central Laboratory eCRF panels).
- Local laboratory testing information (Local Laboratory eCRF panels).

The following derivations will be made based of the eCRF reported results:

- A result will be considered out of range if the observed result is less than the lower limit of the normal range (indicated as "L") or larger than the upper limit of the normal range (indicated as "H"). The normal range is provided by the central laboratory.

- A result is considered clinically significant if indicated as such by the Investigator on the eCRF.
- Quantitative laboratory measurements reported as “< X”, i.e., below limit of quantification (BLQ), or “> X”, i.e., above limit of quantification (ALQ) should be presented in listings as “< X” or “> X” and summarized in summaries as “X”.

8.2.2 Viral Serology

See Table 11 for the viral serology assessments to be performed by the central laboratory. This information should be summarized with descriptive statistics (n[%]) only.

8.3 Inhibitor/Antibody Development (Immunogenicity)

Subject listings will be presented for the following items using the ENR:

- Total binding antibodies to FVIII, PEG and CHO protein.
- Inhibitory antibodies to FVIII.
- Subjects included in the immunogenicity analysis for inhibitory antibodies.

Summary tables will be presented for immunogenicity SAS by age group.

Results on inhibitory antibodies to FVIII and binding antibodies to FVIII, PEG-FVIII and PEG (both Immunoglobulin G [IgG] and immunoglobulin M [IgM]) and anti-CHO antibodies are obtained from the central laboratory.

A subject will be considered to have developed inhibitory antibodies to FVIII if the following criteria are all met:

- Result obtained from the central laboratory are ≥ 0.6 BU.
- Inhibitor is documented at 2 separate timepoints within a 2- to 4-week period at the central laboratory.

The following derivations will be made based of the central laboratory results:

- A low titer (responder) inhibitor is defined as ≥ 0.6 BU but ≤ 5 BU.
- A high titer (responder) inhibitor is defined as > 5 BU.

For the purpose of analyses, positive will be considered a worse result than a negative result.

The proportion of subjects who developed inhibitory antibodies to FVIII at any time during the study will be reported, together with exact Clopper-Pearson 95% CIs for the proportion. The subset of subjects included in this analysis are the subjects that developed inhibitory antibodies to FVIII at any time during the study, and any subject that did not develop any inhibitory antibodies to FVIII but had a FVIII inhibitory antibody test result from the central laboratory.

The following SAS® code can be used in the Clopper-Pearson analysis:

```
PROC FREQ Data = <Dataset>;  
  Weight <Count>;  
  Tables <Result> / BINOMIAL (EXACT CP) ALPHA = 0.05 CL;  
RUN;  
QUIT;
```

where <Dataset> refers to the input dataset, <Count> the number of subjects with particular result and <Result> the actual result (for example “Yes” or “No”).

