9.2.2 Exclusion Criteria for Newly Recruited Subjects

Newly recruited subjects who meet **ANY** of the following criteria are not eligible for this study:

1. Subject has detectable FVIII inhibitory antibodies (≥ 0.6 BU using the Nijmegen modification of the Bethesda assay) as confirmed by central laboratory at screening
2. Subject has a history of confirmed FVIII inhibitors with a titer ≥ 0.6 BU (as determined by the Nijmegen modification of the Bethesda assay or the assay employed with the respective cut-off in the local laboratory) at any time prior to screening

3. Subject has been diagnosed with an inherited or acquired hemostatic defect other than hemophilia A (e.g., qualitative platelet defect or von Willebrand's disease)
4. The subject's weight is <35 kg or >100 kg
5. Subject's platelet count is <100,000/mL
6. Subject has known hypersensitivity towards mouse or hamster proteins, PEG or Tween 80
7. Subject has severe chronic hepatic dysfunction [e.g., ≥ 5 times upper limit of normal ALT and/or AST, as confirmed by central laboratory at screening, or a documented INR >1.5]
8. Subject has severe renal impairment (serum creatinine >1.5 times the upper limit of normal)
9. Subject has current or recent (<30 days) use of other pegylated drugs prior to study participation or is scheduled to use such drugs during study participation
10. Subject is scheduled to receive during the course of the study, a systemic immunomodulating drug (e.g., corticosteroid agents at a dose equivalent to hydrocortisone greater than 10 mg/day, or α -interferon) other than anti-retroviral chemotherapy
11. Subject has participated in another clinical study involving an IP or investigational device within 30 days prior to enrollment or is scheduled to participate in another clinical study involving an IP or investigational device during the course of this study
12. Subject has a medical, psychiatric, or cognitive illness or recreational drug/alcohol use that, in the opinion of the investigator, would affect subject safety or compliance
13. Subject is a member of the team conducting this study or is in a dependent relationship with one of the study team members. Dependent relationships include close relatives (i.e., children, partner/spouse, siblings, parents) as well as employees of the investigator or site personnel conducting the study.

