13. ASSESSMENT OF SAFETY INCLUDING IMMUNOGENICITY

13.1 Immunogenicity

Immunogenicity of BAX 855 will be assessed prior to the infusion of BAX 855 following a washout period^{xi} by measurement of the following antibodies (see also Section 21.4 for the timepoints):

- Inhibitory antibodies to FVIII, using the Nijmegen modification of the Bethesda assay
- Binding antibodies to FVIII, BAX 855, and PEG. Both IgG and IgM antibodies will be measured using an enzyme-linked immunoabsorbent assay (ELISA) assay
- Anti-CHO antibodies measured by an ELISA assay

In addition to the timepoints as described in Section 21.4, the subject should be evaluated for inhibitory and binding antibodies to FVIII, BAX 855, and PEG if clinically indicated, e.g., lack of response to treatment.

A low titer (responder) inhibitor is defined as ≥ 0.6 BU but ≤ 5 BU. A high titer (responder) inhibitor is defined as > 5 BU by Nijmegen modification of the Bethesda assay. Inhibitors must be documented at 2 separate timepoints within a 2- to 4-week period at a central laboratory. Every confirmed FVIII inhibitor ≥ 0.6 BU at the central laboratory must be reported as an SAE.

Based on the variability of the binding antibody tests, only samples with titers $\geq 1:80$ can be confirmed and will be evaluated as positive.

FVIII IgG subclass 1-4 and IgA (using ELISA) may be assessed only if clinically indicated, e.g., in case of lack of response to treatment. IgE antibodies to FVIII and PEG-FVIII (using ImmunoCaps, Thermo Fisher) may be assayed as clinically indicated, e.g., in case of hypersensitivity reactions.

The assay for antibodies to CHO protein will use CHO protein derived from cultures of untransfected cells. Testing for binding of anti-CHO protein antibodies will be performed on citrate-anti-coagulated plasma using an ELISA employing polyclonal anti-human IgG antibodies. Antibody-containing samples will be identified in a screening assay followed by a confirmatory assay to exclude false positive results.

All assays will be performed in a central laboratory.

^{xi} The washout period will be consistent with the infusion interval according to the treatment regimen provided to the subject.

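### SAP 8.3 counts unresolved positives, and subjects never tested after exposure, as inhibitor-negative, so any error it makes favours the product

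*SAP*

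**What the plan says.** SAP 8.3 sets two conditions, both required, before a subject is a case: "Result obtained from the central laboratory are ≥ 0.6 BU" and "Inhibitor is documented at 2 separate timepoints within a 2- to 4-week period at the central laboratory". The proportion of cases at any time in the study is then given "together with exact Clopper-Pearson 95% CIs for the proportion".

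The denominator is the cases plus "any subject that did not develop any inhibitory antibodies to FVIII but had a FVIII inhibitory antibody test result from the central laboratory". No timing relative to exposure is attached to that test result.

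The tables use the Safety Analysis Set: "Summary tables will be presented for immunogenicity SAS by age group". SAP 4.2 defines it: "The safety analysis set (SAS) is to comprise all subjects in the ENR with at least one BAX 855 infusion". The same section lists the PK-assessment infusion form among the sources for that infusion, so the PK dose alone is enough to enter the set.

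SAP 8.3 has no category for a positive result that was not repeated or was repeated outside the window, and it plans no sensitivity analysis for one.

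**The concern.** Inhibitor development is a central safety outcome for a factor VIII product. Protocol 6.5 reports no inhibitors among 234 previously treated subjects, so few or no cases are likely here. The informative number would then be the upper confidence limit, which depends directly on who counts as a non-event.

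Two kinds of subject count as non-events without evidence that they are:

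- **(a) Not tested after exposure.** A newly recruited subject with only the PK infusion and only a screening sample could not have shown the event.
- **(b) Positive but unresolved.** A subject with a result of 0.6 BU or more and no qualifying second sample is neither confirmed nor refuted, yet is placed with the negatives.

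Both rules can only lower the estimate or its upper limit.

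**Working it through.** **Plan's own figure.** The documents state no expected inhibitor rate and no precision target, so there is none to reproduce. The only usable denominator is the planned 116 randomised (SAP 2.3). It is used below as an assumed set size. The Safety Analysis Set could be larger, because a subject given the PK dose need not go on to randomisation.

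**Step 1: can group (a) exist?**

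- Protocol 21.4 schedules immunogenicity sampling at Screening, not at the PK Assessment, and next at Baseline.
- Protocol 21.2 allows up to 56 days between the PK Assessment and completion of the Baseline evaluations.
- For a newly recruited subject the screening result had to be negative for entry. Protocol 9.2.2 excludes a subject if "Subject has detectable FVIII inhibitory antibodies" at 0.6 BU or above.

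A newly recruited subject lost after the PK infusion and before Baseline, with no termination sample, therefore enters as a non-event on a pre-exposure sample.

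**Step 2: can group (b) exist?** Nominal times come from Protocol 8.2, taking 3 months as 13 weeks and 9 months as 39 weeks.

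- Week 4 to Week 8: 4 weeks, which can meet the rule.
- Week 8 to Month 3: 13 − 8 = 5 weeks.
- Month 3 to Month 4.5: 19.5 − 13 = 6.5 weeks. Visit windows could still bring some of these first-half pairs inside 4 weeks.
- Second half, subject without bleeds (the 7.5- and 10.5-month contacts are by phone): draws at 26 ± 1, 39 ± 2 and 53 ± 1 weeks. The shortest possible gaps are 37 − 27 = 10 weeks and 52 − 41 = 11 weeks.
- No draw is scheduled after Completion/Termination.

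For such a subject in the second half, two positives at successive scheduled draws cannot meet the rule. A first positive at the last visit has no scheduled second sample. Confirmation there depends on an unscheduled repeat draw.

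**Step 3: size.** The exact (Clopper-Pearson) upper limit for x events in n is the 0.975 quantile of Beta(x + 1, n − x). For x = 0 this is 1 − 0.025^(1/n). For n = 116, 1 − 0.025^(1/116) = 3.13%.

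| Scenario (set sizes assumed) | x/n | Rate | Upper 95% limit |
|---|---|---|---|
| As written, no cases | 0/116 | 0% | 3.13% |
| Remove 6 in group (a) | 0/110 | 0% | 3.30% |
| Remove 12 in group (a) | 0/104 | 0% | 3.48% |
| One group (b) positive counted | 1/116 | 0.86% | 4.71% |
| Two group (b) positives counted | 2/116 | 1.72% | 6.09% |
| Remove 12 in (a), count one in (b) | 1/104 | 0.96% | 5.24% |

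With no events, group (a) moves the upper limit by 3.30 − 3.13 = 0.17 or 3.48 − 3.13 = 0.35 percentage points. The first group (b) positive moves it by 4.71 − 3.13 = 1.58 points, and the second by 6.09 − 4.71 = 1.38 points.

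**The case against.** **The confirmation rule is the protocol's, not an analyst's choice.** Protocol 13.1 says "Inhibitors must be documented at 2 separate timepoints within a 2- to 4-week period at a central laboratory", and the stopping rule in Protocol 8.6 uses the same 2- to 4-week confirmation. This stands. A positive that is negative on a timely repeat is properly a non-case, and the definition should be kept.

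**Gaps between scheduled visits do not settle the matter.** A reader might infer from Step 2 that every late positive is lost. The documents do not support that. The Protocol 13.1 wording calls for a repeat draw after a positive, the same section provides for extra testing when clinically indicated, and dose-readjustment visits also draw inhibitor samples (Protocol 21.2). What remains is a missed repeat, a repeat outside the window, or a first positive at the final visit.

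**Group (a) is narrow.** A reader might infer that anyone with any test is counted, or that all screening results precede exposure. Neither holds. Never-treated subjects are outside the Safety Analysis Set. The screening result of a transitioning subject comes from the end of an earlier BAX 855 study. Baseline sampling follows the PK dose, and the termination visit, which covers withdrawals, includes an inhibitor test. Only new subjects who leave between the PK infusion and Baseline and also miss the termination sample are affected.

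**The results are listed.** SAP 8.3 lists all inhibitor results and the subjects included in the analysis, so nothing is hidden. But a listing does not correct the headline proportion or its interval.

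**An effect in the other direction is possible.** The numerator covers any time in the study, with no stated condition that the case follow exposure. Entry screening leaves little room for this in new subjects.

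**Conclusion.** The point holds in a limited form. As written, SAP 8.3 counts as negative both new subjects tested only before exposure and subjects whose positive result was not repeated within 2 to 4 weeks. Where these rules matter, they act in the favourable direction.

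It does not follow that the reported inhibitor rate will be too low. With no events, group (a) leaves the rate at 0% and lowers the upper limit by tenths of a point: 0.35 points even if 12 of an assumed 116 subjects are affected. Group (b) lowers the rate only if such positives occur and are real. Each would then be worth about 0.86 points in the rate and 1.4 to 1.6 points in the upper limit. The documents give no count for either group, so the sizes rest on the assumed set of 116 and on the scenarios shown.

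This is a cheap improvement to a safety summary, not a fault that threatens the trial's conclusions.

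**What to change.** Amend SAP 8.3 as follows:

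1. Restrict the denominator to confirmed cases and subjects with at least one central inhibitor result after the first BAX 855 infusion in this study.
2. Keep the protocol's confirmed-inhibitor definition for the main analysis. A positive that is negative on a timely repeat stays a non-case.
3. Report positives not repeated, or repeated outside 2 to 4 weeks, as a separate category and not among the negatives.
4. Repeat the Clopper-Pearson interval counting that category as events, as a sensitivity analysis.

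Counting any two positive results as a case whatever the time between them is not recommended. It would give the SAP a different inhibitor definition from the protocol's.

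The cost is a few sentences in SAP 8.3, one extra table row and a possibly slightly less favourable upper limit. No new data are needed.
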